5.1 Inclusion criteria

Participants eligible for inclusion in this study must meet **all** of the following criteria:

- 1. Signed informed consent must be obtained prior to participation in the study.
- 2. Male and female participants 18 years or older (at the time of the screening visit)
- 3. Presence of NASH with fibrosis confirmed by central reader's evaluation of liver biopsy obtained no more than 6 months before randomization as demonstrated by the following:
 - a. NASH using NAFLD Activity Score (NAS) ≥ 4 with at least 1 point each in inflammation and ballooning on the screening histology assessment performed by the central reader

and

- b. Fibrosis stage 2 or 3 using NASH CRN fibrosis criteria (see Table 8-2 & Table 8-3)
- 4. Able to communicate well with the investigator, to understand and comply with the requirements of the study

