12.4.1 Definition of primary endpoint(s)/estimand(s)

Section 2.1 describes the primary estimands that contain the primary endpoints. This section defines the primary endpoints in detail.

The study uses two primary endpoints.

The first primary endpoint is: Whether (yes or no) the participant achieves improvement in fibrosis by at least one stage without worsening of NASH at week 48 compared with baseline.

One stage fibrosis improvement is defined as the decrease by one point on the NASH CRN fibrosis score, i.e. "from 3 to 2" or "from 2 to 1" (considering that the randomized participants either has stage 2 or stage 3 fibrosis at baseline). Worsening of NASH is determined if any of three components of the NAS score (Steatosis, Lobular inflammation or Hepatocyte ballooning) at Week 48 is greater than that at baseline (FDA definition).

The second primary endpoint is: Whether (yes or no) the participant has resolution of NASH and no worsening of fibrosis at week 48 compared with baseline.

[figure not shown]
Resolution of NASH is satisfied if the NAS score for lobular inflammation ≤ 1 AND the NAS score for Hepatocyte ballooning = 0, regardless of the value for steatosis (FDA definition). Worsening of fibrosis is defined as an increase in the NASH CRN fibrosis score from baseline to Week 48, i.e. "from 2 to 3", "from 2 to 4", or "from 3 to 4".

The two binary primary endpoints will be summarized as odds ratios for pairwise comparisons between treatments.

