12.4.2 Statistical model, hypothesis, and method of analysis

The main goal of the study is to reveal the efficacy of the combination therapy (tropifexor + licogliflozin) compared with placebo in the two primary endpoints, so the two tests of combination therapy vs. placebo (one for each endpoint) will be conducted first. The study will be considered successful if at least one of these two tests passes with statistical significance. An overall two-sided 5% (one-sided 2.5%) alpha is adopted to the study and is splitted evenly to the two primary endpoints. In addition to the comparison between combination therapy and placebo, another four pairwise comparisons may be evaluated for each primary endpoint, rendering a total of ten ([1+4]*2=10) potential comparisons. Each primary endpoint will have its own branch of tests and may pass its alpha to the other branch from its last two tests. Under each branch, the two monotherapies (LJN452 and LIK066) will be compared with placebo after the combination treatment shows superiority over placebo with significant evidence. If one of the monotherapy vs. placebo tests succeeds, then it will pass its alpha to the corresponding combination vs. monotherapy test. An alpha recycling graph (Bretz et al 2009) is presented in Figure 12-1 below to illustrate the test relationship.

Figure 12-1 An alpha recycling graph

Within each primary endpoint branch, five comparisons may be evaluated in the following levels:

- Combination vs. placebo
- Tropifexor (LJN452) vs. placebo; licogliflozin (LIK066) vs. placebo
- Combination vs. tropifexor (LJN452);
- Combination vs. licogliflozin (LIK066);

Since there are two primary endpoints, a total of ten comparisons may be tested.

The comparisons are based on the four arms of the study: one combination therapy arm, two monotherapy arms and one placebo arm. The proportions of histological responders in these four arms are assumed following binomial distributions (n, p). The sampling distribution of the difference $\hat{p}_{m_{_i}} - \hat{p}_{m_{_j}}$ will be asymptotically normal with mean $p_{m_{_i}} - p_{m_{_j}}$ and variance $\frac{p_{m_i}(1-p_{m_i})}{n_{m_i}} + \frac{p_{m_j}(1-p_{m_j})}{n_{m_j}}$, where *m* is the index of the primary endpoint (m = A if the

Novartis	Confidential
Amended Protocol Version 02 (Clean)	

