Combination vs. placebo (test 1, k = 1, i = Cmb, j = Plc)

Tropifexor (LJN452) vs. placebo (test 2, k = 2, i = LJN, j = Plc); licogliflozin (LIK066) vs. placebo (test3, k = 3, i = LIK, j = Plc)

Combination vs. tropifexor (LJN452) (test 4, k = 4, i = Cmb, j = LJN); combination vs. licogliflozin (LIK066) (test 5, k = 5, i = Cmb, j = LIK)

There are ten potential tests to be performed for the two primary endpoints (five for each primary endpoint), and it is important to control the overall Type I error rate for these tests. The alpha recycling graph presented in Figure 12-1 shows how alpha transfers among them. If the data fails to reject the null hypothesis of a test, then the alpha of that test will not be passed to others. This restriction ensures the control of overall Type I error rate. Again, for the primary

Confidential

Amended Protocol Version 02 (Clean) Protocol No. CLJN452D12201C endpoints, the overall alpha is set at two-sided 5%. A logistic regression model with the logit of probability for histological response as the dependent variable, treatment groups as the main effect, baseline fibrosis stage and T2DM (No/Yes) as explanatory variables, and the baseline BMI as a covariate will be utilized to test the hypotheses at each step. While this model will be the typical logistic regression in most cases, it should be set as the Firth logistic regression if some arm (such as the placebo) has a low response rate, as the Firth method returns less biased results for data with rare events. The null hypothesis of *k*th test, if executed, will be rejected if the p-value for the coefficient of treatment effect in the *k*th comparison is less than or equals to its corresponding alpha. If no alpha is passed to a specific comparison, then its corresponding test will not be performed and p-value will not be calculated. More statistical specifications of the model will be described in the statistical analysis plan (SAP).

The number and percentages of histological responders at week 48 in FAS will be summarized by treatment groups. The difference between the treatment of interest and the alternative treatment will be presented along with 95% confidence interval calculated based on the normal approximation for distribution of the difference between two binomial random variables.

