12.8.1 Primary endpoint(s)

Assumptions about true histological response rates for various treatments and placebo are made for sample size calculation. Published studies so far (Table 12-2) suggest unignorable placebo effect ranging from 8% to 18% for different populations and endpoints, but unpublished studies indicate some even higher placebo rates. For each primary endpoint, the response rates of the two monotherapies are assumed to be similar to each other and higher than that of placebo, and the response rate of the combination therapy is deemed to be the highest.

Novartis Amended Protocol Version 02 (Clean) Confidential

Table 12-2	Placebo effects on histological responses

Table 12-2 Placebo effects of histological responses					
Histological Response definition	Time point	Histological study	NASH population with Fibrosis stages	Placebo response rate	
Fibrosis	Month 18	REGENERATE	F1 + F2 + F3	10.6%	
improvement of 1 stage and no		(2019) Obeticholic acid	F2 + F3	11.9%	
worsening in NASH	Week 52	CENTAUR (2018)	F1 + F2 + F3	10.4%	
		Cenicriviroc			
	Week 52	ARREST (2018)	F1 + F2 + F3	17.5%	
		Aramchol			
	Week 48	STELLAR3 (2019)	F3	13.2%	
		Selonsertib			
	Week 48	STELLAR4 (2019) Selonsertib	F4	12.8%	
NASH resolution with no worsening in Fibrosis	Month 18	REGENERATE (2019)	F1 + F2 + F3	8%	
		Obeticholic acid	F2 + F3	7.9%	
	Week 52	GOLDEN (2016) Elafibranor	F0+F1+F2+F3	9%	

Table 12-3	Response rate setting used for sample size and power calculation	

Treatment	True Response Rate			
Primary Endpoint	Combination	LJN452	LIK066	Placebo
At least one stage improvement in fibrosis without worsening of NASH	35%	30%	30%	20%
NASH resolution without worsening of fibrosis	25%	20%	20%	10%

Table 12-3 shows the assumed response rates of treatments and placebo under the two primary endpoints. Since both endpoints involve fibrosis and NASH, it is reasonable to expect these endpoints associated with each other. The participant level correlation of the two endpoints is set at +0.5 to be conservative in evaluating sample size and power.

Sample size is first determined by reaching 80% power for passing the combination therapy vs. placebo test on at least one of the primary endpoints under equal allocations of the four arms. Table 12-4 displays the powers under various sample sizes. From the table, it is clear to see that a sample size of 380 can obtain 80% power for the tests of interest.

Confidential

Amended Protocol Version 02 (Clean)

 Table 12-4

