# 2.3 Patient disposition, demographics and other baseline characteristics

Demographics and baseline characteristics listed below will be summarized by study treatment on FAS.

- Age (years): per demographics CRF
- Age Group: two categories derived for age <65 years or age  $\ge 65$  years
- Gender: per demographics CRF
- Region: derived based on country of study site (Section 2.1)
- Ethnicity: per demographics CRF
- Race: per demographics CRF
- Height (cm) at screening visit
- Body Weight (kg)
- Waist circumference (cm)
- Hip circumference (cm)
- BMI

- Liver function (ALT, AST, ALP, GGT, TBL): see Section 2.1.1 for special baseline definition
- Steatosis stage (0, 1, 2 or 3) based on liver biopsy: categorical data summary
- Lobular inflammation stage (0, 1, 2 or 3) based on liver biopsy: categorical data summary
- Hepatocyte ballooning stage (0, 1 or 2) based on liver biopsy: categorical data summary
- NAS score (Section 5.3.8) based on liver biopsy: continuous data summary
- Fibrosis stage based on liver biopsy: categorical data summary for score 2 and 3
- Hepatic fat fraction based on MRI-PDFF
- Fasting lipids (HDL-C, LDL-C, VLDL-C, triglycerides, free glycerol, free fatty acid, total cholesterol, ApoA1)

Relevant medical histories up to baseline, including NASH specific co-morbidities, will be summarized by system organ class, preferred term and by study treatment on FAS.

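### Adding baseline ballooning and lobular inflammation to the NASH-resolution model is a near-free improvement that may raise power if those scores are prognostic

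*Protocol*

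**What the plan says.** Protocol 12.4.2 sets out a logistic regression of histological response on treatment group and states that "baseline fibrosis stage and T2DM (No/Yes) as explanatory variables, and the baseline BMI as a covariate will be utilized to test the hypotheses". This one covariate set serves endpoint A (fibrosis improvement without worsening of NASH) and endpoint B (NASH resolution without worsening of fibrosis). SAP 2.5.2 and 5.4.1 use the same three covariates.

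Protocol 12.4.1 and SAP 5.3.11.3 define resolution by two scores: lobular inflammation of 1 or less, and ballooning of 0. Both are read centrally for eligibility. Protocol 5.1 requires a total NAS of at least 4, "with at least 1 point each in inflammation and ballooning on the screening histology assessment". SAP 2.3 lists both among the baseline tables, for example "Hepatocyte ballooning stage (0, 1 or 2) based on liver biopsy: categorical data summary".

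Neither score appears in the logistic model, in the imputation model (SAP 2.5.3, 5.4.2) or in the strata of the Cochran-Mantel-Haenszel analysis (SAP 2.5.4, 5.4.4). Randomisation is stratified by T2DM only (Protocol 6.3.3).

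SAP 5.4.1 argues for fibrosis stage as a likely predictor of response, above all of fibrosis improvement. It does not discuss ballooning or inflammation as covariates. Protocol 12.4.2 leaves further model detail to the SAP. The SAP supplied dates from December 2019 and describes three arms.

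**The concern.** The model contains the baseline of endpoint A but not that of endpoint B. How far a participant stands from resolution is set at entry. Using the score ranges in SAP 5.3.8, someone with ballooning 1 and inflammation 1 needs to lose 1 point. Someone with ballooning 2 and inflammation 3 needs to lose 2 + 2 = 4. A participant with inflammation 1 already meets that half of the definition. It is therefore reasonable to expect the grades to predict resolution.

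In logistic regression, leaving out a prognostic baseline factor moves the treatment odds ratio toward 1 and lowers power. It also leaves chance imbalance in starting activity unadjusted. Endpoint B matters because, in Table 12-4, it is the better powered of the two primary endpoints (0.72 against 0.55 at 95 per arm) and it opens its own branch of later tests.

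**Working it through.** **Inputs.** Alpha: "An overall two-sided 5% (one-sided 2.5%) alpha is adopted to the study and is splitted evenly to the two primary endpoints", so two-sided 0.05/2 = 0.025 per endpoint (critical z 2.24). Rates for combination versus placebo from Table 12-3: endpoint A 35% and 20%; endpoint B 25% and 10%. Allocation 140:80. Correlation: "The participant level correlation of the two endpoints is set at +0.5 to be conservative in evaluating sample size and power".

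**1. The plan's own figures.** The joint response probability in each arm is pA·pB + 0.5·√[pA(1−pA)pB(1−pB)]:
- combination: 0.0875 + 0.5 × 0.2065 = 0.191
- placebo: 0.02 + 0.5 × 0.12 = 0.08

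The test is z = (p1 − p0)/√[p1(1−p1)/n1 + p0(1−p0)/n0], with observed proportions. With 100,000 simulated trials:

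| Allocation | Measure | Stated | Obtained |
|---|---|---|---|
| 95:95 | A / B / at least one | 0.55 / 0.72 / 0.80 | 0.550 / 0.717 / 0.801 |
| 140:80 | at least one | 0.85 | 0.850 |

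The tables are reproduced. They rest on an unadjusted test, so they claim no gain from any covariate. Endpoint B alone at 140:80, which the protocol does not tabulate, has power 0.775 by this test.

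**2. Endpoint B with and without the grades.** Logistic regression at 140 versus 80, with marginal rates held at 25% and 10%. The protocol's covariates are compared with the same set plus ballooning (1/2) and inflammation (1/2/3).

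Assumptions, none of them from the documents:
- 60% at ballooning grade 2
- inflammation 40/50/10% at grades 1/2/3
- the two scores independent, and the existing covariates not prognostic
- no missing data; ordinary rather than Firth likelihood; these two arms only

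The odds ratios against resolution per grade are also assumed, over a range:

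| Ballooning, inflammation | Wald | Likelihood ratio |
|---|---|---|
| 1, 1 | 0.68 → 0.68 | 0.73 → 0.73 |
| 1.5, 1.5 | 0.69 → 0.70 | 0.75 → 0.75 |
| 2, 2 | 0.69 → 0.71 | 0.74 → 0.75 |
| 3, 2 | 0.68 → 0.72 | 0.74 → 0.77 |
| 3, 3 | 0.68 → 0.74 | 0.73 → 0.77 |
| 5, 3 | 0.69 → 0.76 | 0.74 → 0.80 |

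There were 10,000 runs per Wald setting and 8,000 per likelihood-ratio setting. The Monte Carlo standard error of one power is about √(0.7 × 0.3/10,000) ≈ 0.005. Before rounding, the gains are 0.5–2.1 points in rows 2–3 and 3.7–6.9 in rows 4–6. With 30% or 80% at ballooning grade 2, the likelihood-ratio gain at (3, 2) falls to about 2 points.

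**3. Type I error.** Under the null at (3, 2), nominal one-sided 0.0125, rejection rates without and with the grades were 0.014 and 0.014 (likelihood ratio), and 0.005 and 0.007 (Wald). The gain does not come from inflated alpha.

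**4. At-least-one success criterion.** Here one balanced binary activity factor was added to the endpoint B model only (likelihood ratio, 4,000 runs, standard error about 0.6 points on each power):

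| Factor odds ratio | Without → with | Gain (points) |
|---|---|---|
| 2 | 0.817 → 0.822 | 0.5 |
| 3 | 0.823 → 0.836 | 1.3 |
| 5 | 0.816 → 0.845 | 2.9 |
| 8 | 0.818 → 0.848 | 3.0 |

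**5. Room for the terms.** Expected endpoint B responders: 140 × 0.25 + 80 × 0.20 + 80 × 0.20 + 80 × 0.10 = 35 + 16 + 16 + 8 = 75, of whom 8 are on placebo.

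**The case against.** The prognostic strength is assumed, and nothing in the documents supplies it. If each grade carries an odds ratio below 2, the gain is barely visible. Study success needs only one of the two combination-versus-placebo tests, so the gain that counts is the smaller one in step 4. All of this stands, and it is why the point is an improvement and not an error.

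Adding covariates also changes which odds ratio is estimated. The marginal value here is (0.25/0.75)/(0.10/0.90) = 3.0; the conditional value in the simulations was 3.14 at (2, 2) and 3.55 at (5, 3). This stands too and should be stated in the plan, although the planned model already gives an odds ratio conditional on fibrosis stage, T2DM and BMI.

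Parsimony is a fair consideration with about 8 placebo responders, but a weaker objection. The SAP's caution about added terms (5.4.1.1) concerns interactions, Firth estimation is available, and SAP 2.5.2 already has a fallback for non-convergence.

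In the imputation model the change will reach few participants, because Protocol 12.4.3 counts those who stop treatment and have no Week 48 biopsy as non-responders. That is also right. The case there is mainly consistency: SAP 5.4.2 already carries any reduction of the analysis covariates into the imputer.

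**Conclusion.** The omission is real, and the SAP's argument for fibrosis stage covers these two scores equally well. Pre-specifying them costs almost nothing. For endpoint B, power is unchanged if they are not prognostic, rises by about 1–2 points at per-grade odds ratios of 1.5–2, and by about 3–7 points at 3–5 under the assumed grade mix (about 2 points at (3, 2) under two other mixes). For study success the gain is about 0.5–3 points.

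Four stronger readings are not supported:
- **That the plan certainly loses power on endpoint B.** This needs a prognostic strength that the documents do not give.
- **That Tables 12-4 and 12-5 are wrong.** They are reproduced. The gap between 0.775 and the 0.68–0.75 of the logistic model comes from the choice of test; it is there even when the grades have no effect.
- **That the test of the null is invalid.** The type I error is not affected by the omission.
- **That the grades belong in the endpoint A and composite models too.** Neither was calculated. For endpoint A, "Worsening of NASH is determined if any of three components of the NAS score" has increased, so steatosis counts as well, and a participant already at the top grade cannot worsen. A high grade may therefore help on A while hindering on B.

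**What to change.** Before unblinding, when the SAP is updated for the four-arm design:
- In the endpoint B model, add baseline ballooning grade and baseline lobular inflammation grade as main effects, or total NAS as a single term. Total NAS saves a degree of freedom but brings in steatosis, which is not part of resolution.
- Add the same terms to the endpoint B imputation model.
- Keep the existing convergence fallback, and say where the new terms come in the order of removal.
- State that the reported odds ratio is conditional on these covariates.

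Endpoint A and the composite need no change on this account. The cost is wording plus one or two degrees of freedom, against about 75 expected endpoint B responders over four arms. No new data, visits or participants are needed.

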12.4.3 Handling of remaining intercurrent events of primary estimand

Intercurrent events of primary estimand will be addressed with various strategies (given that these events occur before the histological assessments at Week 48):

- 1. Bariatric surgery: participants who have undergone bariatric surgeries during trial participation are considered as non-responders (composite variable strategy).
- 2. Use of alcohol above protocol permitted amount: the intercurrent events (overuse of alcohol) will be ignored for estimation (treatment policy strategy).
- 3. Addition or removal of any medication that may have a confounding effect on the endpoints: the treatment effect will be assessed with the intercurrent event ignored (treatment policy strategy). The treatment policy strategy may not be ideal if the confounding medications highly affect the endpoints. Consequently, a supplementary analysis will be conducted where the treatment effect is imputed as if the intercurrent event doesn't occur (hypothetical strategy)
- 4. Premature discontinuation of study treatment due to tolerability, efficacy, adherence, or adverse event: participants who discontinue the treatment after Week 24 will be asked to have their biopsies assessed at Week 48 regardless of the intercurrent event (treatment policy strategy), participants who discontinue the treatment before Week 24 will be considered as non-responders (composite variable strategy), and participants who have no biopsy extracted at Week 48 will be considered as non-responders (composite variable strategy).
- 5. Death, transplantation and other clinical outcomes: participants will be considered as non-responder (composite endpoint strategy).
- 6. Acute medical condition not related to the study treatment affecting the liver: participants will have their Week 48 biopsies assessed regardless of the intercurrent events (treatment policy strategy).
- 7. Acute medical condition related to the study treatment affecting the liver: participants are considered as non-responder (composite endpoint strategy).

Novartis	Confidential	Page 139 of 160
Amended Protocol Version 02 (Clean)		Protocol No. CLJN452D12201C

12.4.4 Handling of missing values not related to intercurrent events

While not possible to confirm missing completely at random (MCAR), the histological response status from the early termination visit after at least 24 weeks of study treatment will be used for the primary analysis in case of missing primary endpoint at week 48. Participants otherwise with primary endpoint missing or any primary endpoint after intercurrent events will have the values imputed using multiple imputation (MI) methods (Rubin 1976, Rubin 1987) under a missing at random (MAR) assumption.

For multiple imputation: an arbitrary missing pattern will be assumed and a fully conditional specification (FCS) method with logistic regression will be applied. The logistic model will be used to analyze the multiple imputed datasets, and pooled results will be obtained based on Rubin's combination rules. More implementation details of the multiple imputation (MI) will be specified in the SAP.

The proportion of participants with missing primary endpoints at week 48 will be compared among the combination therapy, monotherapies and the placebo.

